# Aim 2: Evaluate whether HIV testing combined with PrEP and ART use among male partners increases effective post-partum ART use among HIV-infected Ugandan women in PMTCT B+.

Pregnant HIV-positive women may be more likely to continue ART after delivery and have higher adherence post-partum if their partners are tested, there is mutual disclosure of HIV status, and their partner takes ART or PrEP, depending on his status. We will evaluate ART use and viral suppression at 12 months post-partum among the 500 HIV-positive pregnant women who are randomized to male partner testing strategies (Aim 1). In this observational analysis, we will use causal inference methods to assess whether the outcome (women's viral load at 12 months post-partum) is improved by the exposure (male partner testing and engagement in HIV care or prevention – PrEP use among HIV-negative men and ART use among HIV-positive men).

The primary outcome is viral suppression at 12 months, as a measure of the woman's effective ART use in the first 12 months post-partum and her adherence. Viral suppression will be defined as plasma viral load <400 copies/ml) at 12 months post-partum. Secondary outcomes include: a) post-partum adherence, as measured by pharmacy records will be used to measure ART dispensation and women's self-report about treatment interruptions; b) infant HIV status at 6 weeks as determined by PCR results(HIV-infected/uninfected);and c) infant survival at 12 months as reported by the mother.

# Aim 3: Assess the acceptability of HIV self-testing and PrEP as well as the perceptions of ART adherence and HIV status disclosure during the COVID-19 pandemic, for pregnant women taking part in PMTCT B+ and their male partners, using qualitative and quantitative methods.

PMTCT B+ has the secondary benefit of reducing HIV transmission to male partners if HIV-positive women continue antiretroviral therapy (ART) long-term with high adherence. However, optimizing the effectiveness of PMTCT requires understanding factors that influence low uptake of HIV testing by male partners (~1/5 of partners of women in Uganda PMTCT programs are tested for HIV. In addition, previous studies have indicated that 1/3-1/2 of African women discontinue ART after delivery, and the importance of disclosure and partners' engagement in HIV care or prevention need to be assessed to determine how much those factors influence ART continuation post-partum. During the COVID-19 pandemic, both adherence to ART and initiation of HIV status disclosure may be greatly impacted.

We will use quantitative and qualitative methods to investigate acceptability of HIVST and PrEP. Additionally we may explore the perceptions of COVID-19 and the intersections on status disclosure, male partner testing, and access to and experiences of HIV prevention and treatment during the pandemic. Quantitative behavioral data will be collected from the study cohort during clinic visits using multiple validated questionnaires. A structured interview administered to all HIV-infected female partners at enrollment will ask about knowledge of the partner's HIV status, disclosure, fertility desires, relationship power, and intimate partner violence. Up to 110 individual interviews will be conducted. A purposefully selected subsample of up to 90 individuals will take part in qualitative in-depth interviews to achieve in-depth understanding of the acceptability of HIV self-testing and PrEP use by male partners to women in PMTCT B+ and to male partners. In a sample of 10 PMTCT providers, we will assess perspectives about HIVST, facilitated disclosure, male partner linkage to HIV care, and women's ART use post-partum.

The goal of the qualitative analysis is to assess the acceptability of HIV self-testing and PrEP use by pregnant women in PMTCT B+, their male partners, and implementation perspectives of PMTCT providers.

#### Population

Five hundred HIV-positive pregnant women, ≥18 years of age, with male partners of unknown status, will be recruited from PMTCT B+ programs in Kampala. Women in the intervention arm will receive HIVST kits to give to or use with their partner. Women in the standard of care arm will receive invitation letters that invite the male partner to be tested at the clinic where their pregnant partner receives antenatal care, or at IDI Kasangati.

#### Eligibility

For all participants

- Able and willing to provide written informed consent
- Able and willing to provide adequate locator information for study retention purposes

#### For women

- Age ≥18
- Currently pregnant
- HIV-positive based on positive rapid HIV tests, according to national algorithm
- Not currently enrolled in an HIV treatment study
- Male partner not known to be HIV-positive orhas not tested in the past 3 months

#### For men

- In partnership with an HIV-positive pregnant woman in PMTCT B+

#### Sample size

A total of 500 HIV-positive pregnant women and their male partners.

#### Recruitment

IDI Kasangati has long-established recruitment and retention strategies to identify and enroll research-naive participants for prospective follow up. Recruitment materials will be approved by the IRB before study initiation. Recruitment materials will educate women about the benefits of male partner testing, the probability of being HIV serodiscordant, and risks of post-partum ART discontinuation for the woman's health and the possibility of HIV transmission to her baby and partner.

Women attending antenatal care are offered HIV testing, and those who test positive are provided immediate ART according to Uganda national HIV treatment and prevention guidelines. Approximately, 50 HIV-positive women are identified per month. IDI Kasangati will work directly with collaborating health facilities, including antenatal care/PMTCT programs, to identify pregnant HIV-positive women attending PMTCT B+. Health care workers and study staff at collaborating clinics will provide general information sessions to inform potential participants.

#### Study screening

Women will be enrolled and followed at collaborating ANC clinics. Trained research staff will counsel potentially eligible women about the benefits of male partner testing, post-partum ART persistence, and possible participation in the study. Counseling messages will include:

Reasons for male partners to be tested for HIV:

- To know his status.
- If he is infected that he does not infect others.
- If he is positive, to help him to access care and treatment which will help him stay healthy longer.
- If he is negative, to help him stay HIV negative.
- To strengthen their relationship.
- To avoid testing by proxy since about half the time, he will have a different status than his partner.

HIV status disclosure:

- Does your partner know your status?
- If no, and you are positive, what do you think might happen if you discuss this with your partner?
- Where would you tell him? When would you tell him?
- Encourage women to tell him a story about the antenatal clinic, how other women have encouraged their partners to test for HIV, which has been beneficial for the family by keeping both partners health longer and see what kind of reaction he has.
- Importance of talking about HIV together with their partner so they can plan for the future.
- Risk of HIV for their children.
- Explore the possibilities of being sent away, relationship ending, violence, etc.

#### Intimate partner violence:

The counselor will collect the following information in a culturally appropriate way.

- In the past month, has your current partner punched, slapped, kicked, bit you, or caused you any type of physical harm?
- In the past month, has your current partner insulted, ignored or humiliated you, yelled at you, or made you feel ashamed or bad about yourself?

- In the past month, has your current partner forced you to have sex or perform any sexual act, or touched you sexually in any way that you did not want?
- In the past month, has your current partner made you feel afraid, unsafe or in danger?
- In the past month, has your current partner taken your money when you didn't want him to, or prevented you from working outside the home?

Women who indicate a willingness to participate will provide independent informed consent for study screening. Male partners who self-test for HIV and come to clinic for confirmatory testing or come for HIV testing in response to an invitation letter will be offered the opportunity to consent for screening. Men will consent to participate in the study and receive open label PrEP or ART, depending on HV status. Participants will be asked screening questions about their medical history, including specific questions about prior pregnancies, any medical problems, partner's status, HIV testing, and whether they think violence would result from offering a HIVST kit to their partner.

#### Study enrollment

Each participant will be asked to provide independent informed consent for study participation. Women who meet eligibility criteria and are willing to participate in the study for 12 months postpartum, will be consented and enrolled. Trained clinicians will perform physical exams, including measurement of blood pressure, height, and weight.

#### Study procedures

#### Specific study procedures are depicted in Figure 3 and detailed in Tables 5-7. Figure 3: Study Procedures for HIV+ Pregnant Women in PMTCT B+

#### Female partner randomization

HIV-positive pregnant women will be randomized in a 2:1 ratio to provision of HIVST kits to use with their male partners or to take an invitation letter to their male partner to be tested at their ANC clinic, or if the male prefers, IDI Kasangati. The 2:1 randomization provides more data on male partner testing with HIVST, which would be useful in assessing uptake, social harms, and

linkage to PrEP and ART. There is ample historical information about male partner testing with invitation letters; the objective of this protocol is to maximize the learning about implementation and outcomes with secondary distribution of HIVST through PMTCT B+.

The randomization code and resulting randomization list will be generated and maintained by the study statistician or designee. A variable size block randomization scheme will be implemented to produce the randomization list and maintained by the study biostatistician. Thus, neither participants nor study staff will be blinded to each participant's randomization group assignment.

#### HIVST intervention group

Pregnant women will be provided a brief demonstration of how to use the self-test, and will be given two oral fluid based HIV self-tests (Oraquick rapid HIV-1/2 test kit with developer fluid vial and stand) to take home with written and pictorial instructions translated into Luganda (the local language) about HIVST to share with their partner. The instructions will clearly indicate how to perform an oral swab, how long to wait to read results, and how to interpret the results. Women will receive information about HIV self-testing including reasons for suggesting usage of the self-test to their partner, and strategies for introducing self-tests to their partners; however, it will also be emphasized that women are under no obligation to suggest to their partner or convince him to use the self-test. Because use of self-tests at home will mean that a trained counselor will not be present when women or their partners take the test, the counselor will discuss with women what messages might best suit her situation, so that she and her partner can use the self-tests correctly and safely on their own. A counselor will be available by phone if a woman in the self-test arm needs help explaining counselling messages to their partner. The messages and counseling that we will provide will adhere to Uganda National Guidelines for HIV Testing Services [70].

#### Counseling messages:

- Knowing your partner's status will help you make better decisions to protect your partner and unborn children from HIV.
- This HIV self-test kit is an HIV test that you can use at home. We will show you how to use it, and you can take it home today to use yourself and to give to your partner to use.
- We are giving you 2 HIV self-test kits and encourage you to give one to your partner, and use the second one for yourself, so that you test together.
- We will ask if you have any questions or concerns about how you might want to talk to your partner about using the HIV self-test. If you think he may react violently, you should not bring up the topic with him or wait for an opportune time to do so.
- This is how you could introduce the self-test kits to your husband/partner:
  - a) Place the test kit where he is most likely to see it. When he inquires about it, say you went to the clinic and was taught about the new self-test-kit ... and it is a good opportunity to test together.
  - b) Gauge his mood, and if it is good, ask him about the last time he was tested/you tested as a couple, then tell him you were given HIV self-tests at the clinic and it is a good opportunity to test together.

- c) Ask him whether he has heard about the new HIV test kit which uses oral fluid... then you could tell him that you were given some kits and it would be a good opportunity to test together and know each other's HIV status.
- If your partner agrees to self-test either with you or alone, remember that the test result is preliminary and should be confirmed at the clinic.
- After you or your partner uses the self-test kit, you can keep the used test kit(s) until you return the used test kit to the clinic.
- You are not required to use the test kits; it is a choice. It is also not mandatory to bring the used test kit back.

Counselors will provide tailored messaging about HIV concordant positive or serodiscordant results, additional counseling as needed, encourage joint prevention decision making, and facilitate linkage to HIV prevention, treatment and care services.

Each HIVST kit will include positively framed messages, informational materials, and a voucher with unique identifying numbers for men who use the self-test to come to a clinic for confirmatory testing. Test kits will also clearly indicate a 24-hour "helpline" to call in case questions arise about how to use the tests, obtain support in case of a reactive test, where to go for confirmatory testing, or where to seek additional counseling; this helpline will also be useful for providing additional support and referrals to women who may experience social harms.

In addition, we will provide a brief educational sheet about the importance of their HIV testing as a first step; if they are HIV-positive they can stay healthy by taking ART and if they are HIV-negative, they can remain HIV negative and healthy by taking PrEP. Both will help be beneficial for them and their family.

Returned test strips will be used to verify use and not HIV test results.

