### Minimizing probability of violence associated with participants' offering HIV testing to sexual partners:

To minimize the likelihood of social harms, including violence against HIV-positive pregnant women participants, trained study staff will talk to participants at the time of enrollment about the importance of *using their discretion* and *assessing the risk of intimate partner violence (IPV)* when deciding whether to introduce self-testing to their partners. Study staff will also talk to participants about strategies for introducing self-testing or voluntary counseling and testing (VCT) referral voucher to partners, including talking points. It will be emphasized to study participants that they are not obligated to distribute self-tests to their partners. Participants will be counseled to never offer a self-test or invitation letter to a partner who they will believe will become violent due to introducing HIV testing.

Having developed the training materials for study staff and implemented the intervention successfully in the Kenya pilot study, we are confident that these procedures help minimize the risks of social harms and intimate partner violence. We will also provide study participants with information on where they can seek help if they do experience violence or do need advice. We will establish a support telephone line (hotline) that study participants or their sexual partners can call at any time that will put them in touch with the study coordinator. The study coordinator will help arrange support for any woman experiencing violence. In our pilot study we set up a hotline similar to what is proposed here.

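### The kit-arm counselling script and the violence-minimisation section give different instructions on expected partner violence, and no stated step before handover depends on the violence-screen answers

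*Protocol*

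**What the plan says.** Four places in the Protocol bear on this.

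- **Counseling messages, under HIVST intervention group.** For a woman who thinks her partner *may* react violently, the message is "you should not bring up the topic with him or wait for an opportune time to do so". The next bullet lists three ways to introduce the kit. The first is "Place the test kit where he is most likely to see it"; the second depends on his being in a good mood; the third opens by asking whether he has heard of the oral-fluid test.
- **Minimizing probability of violence (the violence-minimisation section).** "Participants will be counseled to never offer a self-test or invitation letter to a partner who they will believe will become violent". The section also asks staff to discuss discretion and the assessment of violence risk at enrollment.
- **Study screening, Intimate partner violence.** The counselor collects five past-month items, for example "In the past month, has your current partner made you feel afraid, unsafe or in danger". The general screening questions add "whether they think violence would result from offering a HIVST kit to their partner".
- **Eligibility, For women.** There are five criteria, none about violence. The last is "Male partner not known to be HIV-positive orhas not tested in the past 3 months".

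The SAP does not mention violence or social harm.

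**The concern.** The women concerned are those at highest risk from the intervention. The Protocol's background section on self-testing kits in PMTCT B+ itself expects social harms to be possibly more likely when a man learns that his partner is HIV-positive. A counsellor following the kit-arm script may tell such a woman that she can defer the conversation. A counsellor following the violence-minimisation section tells her not to make the offer at all. Both are following the Protocol.

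The information needed to identify these women before handover is already collected, but the Protocol does not say what it is for. The Protocol also gives learning about social harms as one reason for the 2:1 allocation. Reports of harm are harder to interpret if it is not fixed what women at risk were told.

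**Working it through.** No arithmetic applies. The check has two parts.

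**1. Do the two instructions match?**

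| | Counseling messages | Violence-minimisation section |
|---|---|---|
| Trigger | she thinks he *may* react violently | she believes he *will* become violent |
| Instruction | do not raise it, or wait for a better moment | never offer |
| Item covered | the self-test | self-test or invitation letter |
| Arm | kit arm | both arms |

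- The first option in the counselling message agrees with the violence-minimisation section. The second does not: waiting for a better moment permits a later offer, which *never* rules out.
- The sentence can also be parsed so that *should not* governs both verbs, which would tell her not to wait either. A spoken script that can be read both ways does not settle the matter.
- Suppose the two triggers are meant as two grades of risk. A woman who believes he *will* become violent also thinks that he *may*, so both instructions still reach her. Nothing says that one overrides the other.
- The introduction strategies that follow carry no exception for a woman to whom the violence message applies.

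**2. Does any stated step before handover depend on the screening answers?**

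| Place | Action conditional on the answers |
|---|---|
| Eligibility (all participants; women) | none |
| Study enrollment | none |
| Female partner randomization | none |
| HIVST intervention group and Counseling messages | none; women in this arm are given two kits |
| Partner invitation group | none |
| Table 5, procedures for women | no row for the screen or its review |

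The safeguards found elsewhere are of two kinds:

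- *Given to all women:* exploring possible violence in screening counselling; tailoring messages to her situation; no obligation to distribute; a helpline.
- *Acting once violence or harm has occurred:* support arranged by the study coordinator for a woman experiencing violence; counselling and referral when social harms occur.

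None is tied to the screening answers. Figure 3 (women's procedures) and the consent pages are not in the text available, so this absence is established only for the readable text and tables.

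**The case against.** The strongest reply is that the passages can be read together: one covers possible violence and the other expected violence, the first option in the script agrees with the stricter section, and tailored counselling fills the gap. That narrows the conflict to the second option and the trigger. It does not remove it, because the Protocol never says that the two are graded.

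Several stronger readings are tempting, and the documents do not support them.

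- *Letter-arm women hear nothing about violence.* The Partner invitation group section is silent, but the violence-minimisation section addresses all participants and names the invitation letter. Only the extra sentence in the script is specific to the kit arm.
- *The screen has no effect at all.* Violence is explored with every woman and messages are tailored. What can be said is that no stated action is conditional on the answers.
- *Women who fear violence are told to leave the kit in view.* That suggestion belongs to a general list for all kit-arm women. What is missing is an exception.
- *What happens to these women goes unrecorded.* Violence is asked about at enrollment and at follow-up visits. Women whose partners do not come are asked whether testing was discussed and whether harm resulted. What the Protocol does not provide for recording is whether the screening answers were reviewed before handover.
- *A planned violence comparison is biased.* The SAP plans no comparison of violence or social harm between arms.
- *The number affected can be estimated.* The rates of 0.7% to 2.7% in the Risks section are per visit and come from other cohorts, including HIV-uninfected women. They are not the share answering yes to this screen.

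**Conclusion.** The point holds in a limited form. Two safety instructions for the same situation do not match, in the action allowed and in the trigger, and the script lists introduction strategies without an exception. Violence answers are collected at screening with no stated use before the kit or letter is handed over.

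No number can be put on this: the documents give no screen-positive share, and no planned estimate is shown to be biased. The conclusion rests on the natural reading of the counselling sentence (on the other parse it is still ambiguous) and on the readable text, without Figure 3 or the consent pages. The case for acting is participant safety and consistent conduct across counsellors and clinics.

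**What to change.** 1. Reconcile the counselling message and the violence-minimisation section into one instruction, with one stated trigger in place of *may* and *will*. Say how the list of introduction strategies applies to women who meet it. The sponsor and investigators decide which instruction is right.
2. Use the same instruction in both arms, and repeat or cross-refer to it in the Partner invitation group section.
3. State that the counsellor reviews the screening violence answers before handing over the kit or letter, acts under the reconciled instruction, and records on the case report form that the review was done. The screening question names only the kit, so say how it is to be used for a woman assigned the letter.
4. Keep every randomised woman in the intent-to-treat set, whatever her answers.

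The cost is revised script wording, a briefing for counsellors, one form entry and ethics review of the modification. It needs no new visits or exclusions. For women already randomised, only documentation remains possible: state which instruction the counsellors used.
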